Because the current dosing guideline for patients with rheumatoid arthritis do not to exceed 20 mg daily maintenance doses [17], the 20mg/day dose is selected as the safe starting dose. In addition, in personal communications, [name] has used leflunomide at doses of 10-20mg daily for 6 weeks in patients who have failed methotrexate with report of minimal side effects.

Patients will be treated in planned 28-day treatment cycles. Patients may continue to receive cycles of treatment on study until disease progression or unacceptable toxicity, or other criteria for removal from study treatment are satisfied. While on active treatment patients will undergo monthly evaluation for response by mSWAT and the CAILS (composite assessment of index lesion severity) [29, 30]. Following the decision to end leflunomide treatment, all patients will undergo 11 days of treatment with cholestyramine, which fixes the metabolite, preventing re-absorption and effectively lowering drug levels. Cholestyramine has been shown to decrease plasma levels of teriflunomide (A77 1726) in healthy volunteers by approximately 40% in 24 hours and by 49-65% in 48 hours [17].

In addition, molecular correlates and *ex vivo* responses will be evaluated using skin specimens, which will be collected from patients before treatment, after one cycle, four cycles of leflunomide treatment, end of therapy (if lesions are still present), and at disease progression. Molecular correlate analysis of leflunomide response will include single cell RNA sequencing. Specimens derived from before and after leflunomide treatment (after 1 month and at progression or complete response, if possible) will be analyzed, as well as pre-treatment specimens exposed to teriflunomide *ex vivo*.

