9.2.2 Timepoints of collection

Lesion samples will be taken at the following timepoints:

- Pre-dose Cycle 1 Day 1 (baseline samples may be collected anytime post-informed consent and prior to the Cycle 1 Day 1 dose)
- Cycle 2 Day 1, and Cycle 5 Day 1 if lesions are present
- At end of protocol therapy (13 or fewer cycles) if lesions are present.
- At disease progression

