9.2.7 Immunohistochemistry

In addition, immunohistochemistry will be performed on all specimens to better examine the effect leflunomide has on the changing tumor and tumor microenvironment as well as correlate these findings with those from scRNA-seq. Current work in this area has noted that the predominant cells in the tumor microenvironment of CD30+LYPDs include CD163+ M2, tumor infiltrating CD8+ lymphocytes, FOXP3+ Tregs and programmed cell death (PD-1) lymphocytes.

The multiplex immunohistochemistry of the tumor microenvironment will distinguish the CD30+ T cells (tumor cells) from other cells (M2, Tregs, tumor infiltrating T cells) and whether or not PD1 co-expression is noted. The findings will be correlated to clinical response.

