- f. End of Treatment (EOT) Day 0 is defined as the day the determination to end treatment is made. EOT Day 0 assessments to be performed as soon as feasible, especially in the event of off treatment due to unacceptable toxicity and no later than 7 days after decision to end treatment; assessments performed after last dose of study agent(s) and within 7 days of the decision to end treatment may serve as EOT Day 0 assessments.
- g. EOT Day 1 is defined as the day cholestyramine administration begins; it will usually follow immediately after EOT Day 0, although it will not be deviation if this does not occur. If it does not follow immediately after EOT Day 0, the rest of calendar will follow per the actual EOT Day 1 (not EOT Day 0). Cholestyramine (8 grams three times daily for 11 days) will be administered according to [Section 5.5](#).
- h. EOT Day 14 assessments must occur after completion of cholestyramine, and may occur on Day 14 +/- 3 day window. If the cholestyramine administration period is extended beyond 11 consecutive days, the EOT Day 14 assessments may occur outside of this defined window.
- i. EOT Day 30 visit has a +/- 2 day window, however this window may be adjusted without deviation to ensure that it corresponds to the final teriflunomide clinical test (see footnote ee). All participants will be followed until resolution or stabilization of any serious adverse events occurring during treatment or starting within 30 days of last study drug administration or within the time to complete the EOT Day 30 assessments, which every occurs later.
- j. Active follow-up will occur for participants who have completed EOT procedures and yet to demonstrate disease progression. Disease response will be assessed every 3 months. Active follow-up will continue for 12 months or until disease progression, whichever is earlier.
- k. Informed consent process to be fully documented: e.g. prospective participant had sufficient time for deliberation, all questions were answered, treatment options provided by MD, full study reviewed including risks, and a copy of signed consent given to participant.
- l. Inclusion/exclusion criteria are detailed in [Section 3](#).
- m. See [Section 4.3](#) for slot reservation and registration process. Treatment must begin within 7 days of registration. Documentation providing Investigator's confirmation that all eligibility criteria are met must be available prior to registration.

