- n. Medical history to include review treatment history for CD30+LYPD medical history pertaining to eligibility, and demographic information.
- o. Vital signs: Weight, heart rate, blood pressure, respiration rate, temp. Height required only at baseline.

- p. Adverse event (AE) reporting begins for events that occur after start of study agent. AE recording and reporting will continue until the completion of the EOT Day 30 visit or until resolution or stabilization of any serious AE occurring before the completion the EOT Day 30 assessments, which every occurs later.
- q. Serum or urine pregnancy test for women of child bearing potential only.
- r. T-Spot or other TB antigen test.
- s. Consent, acute hepatitis panel, to be completed within 30 days prior to registration.
- t. Skin photographs: for subjects with skin lesions, up to five designated index lesions, representative of the subject's extent of disease, will be selected at baseline and measured and photographed using a digital camera. Photos should be taken against a blue backdrop. The photos will be taken on Day 1, prior to the first dose and then Cycle 2 Day 1 (-7 days) then every Cycle. In addition, half-body global photos (waist to feet, waist to top of head and sides) will also be obtained. Photos must be labeled with patient's protocol number and initials.
- u. Modified Severity Weighted Assessment Tool (mSWAT)[30] ([Appendix C](#))
- v. skin biopsies for research will not be taken at baseline if patients have a recent biopsy taken containing needed information.
- w. skin biopsies for research at baseline, at C2D1, C5D1, and EOT (if lesions are present), and at disease progression ([Section 9.2](#)).
- x. CBC with differential: erythrocytes (RBC), hemoglobin, hematocrit, platelets, total WBC plus absolute differential counts (neutrophils, lymphocytes, monocytes, eosinophils, basophils).
- y. Serum chemistry panel: Comprehensive metabolic panel (sodium, potassium, chloride, carbon dioxide, creatinine, urea nitrogen, calcium, glucose, albumin, total bilirubin, alkaline phosphatase, total protein, ALT/SGPT, AST/SGOT) LDH, magnesium, phosphorus, and uric acid.
- z. See [Section 11.2](#) for response assessment criteria.
- aa. Teriflunomide clinical blood assay to be ordered as "leflunomide metabolite" miscellaneous clinical test.

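### Table 10 marks the end-of-treatment research biopsy only at EOT Day 30, after the cholestyramine course, so it samples largely washed-out tissue; the progression biopsy has no column of its own

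*Combined protocol and SAP*

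**What the plan says.** Section 9.2.2 lists the lesion samples. After baseline, Cycle 2 Day 1 and Cycle 5 Day 1 come two further items: "At end of protocol therapy (13 or fewer cycles) if lesions are present" and, on its own line, "At disease progression". Footnote w to Table 10 repeats the list: "skin biopsies for research at baseline, at C2D1, C5D1, and EOT (if lesions are present), and at disease progression". Neither place gives a day within the End of Treatment block.

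The skin biopsy row of Table 10 has three marks: Day 1 of Cycles 1-3, Day 1 of Cycle 4 onward, and EOT Day 30. It is blank at EOT Day 0, Days 1-11, Day 14 and Active Follow-Up. Photographs, mSWAT and response assessment are all marked at EOT Day 0.

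Two footnotes fix the clock. Footnote f: "End of Treatment (EOT) Day 0 is defined as the day the determination to end treatment is made". Footnote g: "EOT Day 1 is defined as the day cholestyramine administration begins". Section 5.5 gives cholestyramine for 11 days to everyone who leaves treatment, and footnote i lets the Day 30 visit move to coincide with the final teriflunomide test.

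On use of the tissue, section 9.2.7 applies immunohistochemistry to every specimen "to better examine the effect leflunomide has on the changing tumor and tumor microenvironment". Section 2.5 adds: "Specimens derived from before and after leflunomide treatment (after 1 month and at progression or complete response, if possible) will be analyzed".

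**The concern.** The text and the calendar give different impressions of when the end-of-therapy sample is taken. The natural reading of 9.2.2 is the point at which leflunomide stops. The calendar puts the sample about a month later, after a procedure whose purpose is to remove the drug. Staff work from the calendar.

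Three things follow.

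- The Cycle 2 and Cycle 5 specimens are taken during treatment, whereas the end-of-treatment specimen is not. It mixes any lasting drug effect with the effect of withdrawal.
- The condition that lesions be present is judged about 30 days after the Day 0 response assessment. A patient clear at Day 0 whose lesions return could then supply an end-of-therapy sample. Section 2.1 says that in lymphomatoid papulosis lesions usually come back once phototherapy or methotrexate is stopped; the documents do not say this of leflunomide.
- Progression ends treatment (section 5.6). Once a patient enters the End of Treatment block, Day 30 is the only biopsy mark left, and for progression during follow-up there is none.

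With 12 to 14 patients, and samples only from those who still have lesions, each specimen is hard to replace.

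**Working it through.** The plan states no figure for this point, so there is none to reproduce. The check has two parts.

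**1. Is the mark really under Day 30?** Reading Table 10 column by column, the neighbouring rows fall where the footnotes say they should. Cholestyramine falls in Days 1-11, teriflunomide testing in EOT Days 14 and 30 (and Cycle 4 onward), and mSWAT in EOT Day 0, Day 30 and Active Follow-Up. On the same count, the biopsy row's single End of Treatment mark is at Day 30. With Day 1 as the first cholestyramine day and an 11-day course, Day 30 is 30 - 11 = 19 days after the course ends.

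**2. How much drug is left at Day 30?**

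Inputs:
- On-treatment teriflunomide at 20 mg/day: mean 42 mg/L, range 3-150 mg/L (section 2.2).
- Fall on cholestyramine in healthy volunteers: "by approximately 40% in 24 hours and by 49-65% in 48 hours" (section 2.5).
- Half-life without cholestyramine: about 14 days (section 2.2).
- In-vitro reference levels (section 2.3): 3-5 µg/mL, which is 3-5 mg/L, for DHODH blockade in CLL cells; 50-200 µmol/L for apoptosis in CD30+ lines.

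Assumptions: the early fractional fall holds for all 11 days, a 14-day half-life applies afterwards, and plasma stands in for skin.

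Fraction left at Day 30 = (fraction left after 11 days of cholestyramine) × 0.5^(19/14), where 0.5^(19/14) = 0.390.

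| Rate used | After 11 days | Day 30 fraction | From 3 mg/L | From 42 mg/L | From 150 mg/L |
|---|---|---|---|---|---|
| 40% per 24 h | 0.60^11 = 0.0036 | 0.14% | 0.004 | 0.06 | 0.21 |
| 49% per 48 h | 0.51^5.5 = 0.0246 | 0.96% | 0.029 | 0.40 | 1.44 |
| 65% per 48 h | 0.35^5.5 = 0.0031 | 0.12% | 0.004 | 0.05 | 0.18 |

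(Last three columns in mg/L.) The ±2-day window changes little: from the mean at the slowest rate, 0.45 mg/L at Day 28 and 0.37 mg/L at Day 32.

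For comparison, 50 µmol/L × 270.2 g/mol = 13.5 mg/L and 200 µmol/L × 270.2 g/mol = 54.0 mg/L, taking the molecular weight in section 8.1.1 for the metabolite as well. Every projected Day 30 level is below 3 mg/L, the lowest active level cited.

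The result depends on the cholestyramine. Without it, Day 30 would be 42 × 0.5^(30/14) = 9.5 mg/L from the mean and 150 × 0.5^(30/14) = 34 mg/L from the top of the range.

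**The case against.** Much of the case against a broader criticism is sound.

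- **Progression sample.** A reader might infer that the plan defers the progression biopsy to Day 30. It does not. Section 9.2.2 and footnote w list it separately, and footnote w is also attached to the Day 1 cycle visits, where on-treatment progression would be found. What remains is that the table gives it no column.
- **Drug-free tissue.** This is too strong. Section 5.5 sets a target below 0.02 mg/L, and if it is missed, further cholestyramine is only to be considered. From the mean, the projected 0.05-0.40 mg/L is about 2.5 to 20 times that target. Largely washed out is as far as the figures go.
- **Comparison with on-drug samples.** The documents nowhere say that end-of-treatment tissue will be compared with Cycle 2 and Cycle 5 tissue as if all were on drug. The written single-cell analysis (9.2.6) pairs baseline with Cycle 2 Day 1. Labels carry the date and timepoint (9.2.4), so later samples can be identified.
- **In-vitro thresholds.** They do not separate on-drug from off-drug tissue cleanly. A patient at 3 mg/L is below 13.5 mg/L while on treatment. Teriflunomide is more than 99% albumin-bound (section 2.4), so total serum and culture concentrations may not be like for like, and no skin concentrations are given. The argument therefore rests on the fraction remaining.
- **Moving the mark.** That alone does not secure an on-drug sample. Footnote f allows Day 0 assessments up to 7 days after the decision to stop, while cholestyramine usually starts straight after Day 0.

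It can also be said that footnote w's EOT covers the whole block, so text and table are merely imprecise. That is fair, but the only day the table offers is the one after washout, and no passage says that a post-washout sample is intended.

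**Conclusion.** The point holds in a limited form. Following Table 10, the end-of-treatment biopsy comes from tissue with roughly 1% or less of the on-treatment plasma level, given a constant fractional fall over 11 days and plasma as a proxy for skin. It cannot show the on-drug effect that 9.2.7 sets out to examine, and lesion presence is judged about a month after the Day 0 response assessment. The progression biopsy is required by the text but has no dedicated place in the table, so it could be taken late or missed.

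The consequence is confined to exploratory tissue work, mainly immunohistochemistry and the progression or complete-response specimens in section 2.5. Overall response, complete response, duration of response, toxicity and CAILS do not depend on it. This is an inexpensive improvement to make, and it does not threaten the trial's main results.

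**What to change.** Reconcile section 9.2.2, footnote w and Table 10:

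1. Move the end-of-treatment biopsy mark from Day 30 to EOT Day 0. State that the sample is collected before the first cholestyramine dose where feasible, since the 7-day window in footnote f does not ensure this, and that drug elimination is not delayed for it.
2. Mark the progression biopsy at the visit where progression is called, on treatment or in Active Follow-Up. Samples from follow-up will be off drug wherever they are marked.
3. Record each specimen as before or after the start of cholestyramine, and summarise the two groups separately in the immunohistochemistry and any later sequencing.

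If a post-washout sample is in fact wanted, say so and give its purpose.

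The cost is a calendar edit and one added data item; the planned number of biopsies does not change. The downside is small: some patients, such as those stopping urgently for toxicity, will have only an off-drug sample.

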9.2.3 Processing details

The collected samples will be processed as follows:

- 1/2 of each lesion will be formalin fixed (FFPE).
- 1/2 of each lesion will be collected in saline.

9.2.4 Labeling of samples

Samples will be labeled with the study number, subject ID, type of biopsy (shave or punch), date and timepoint of collection (as stated in [Section 9.2.1](#)), and if applicable patient initials.

9.2.5 Sample shipment

Samples collected at the above indicated timepoints will be taken to [name] laboratory ([name]) for processing as stated in Figure 9.1.

9.2.6 Single Cell RNA Sequencing

The samples at baseline and beginning of cycle 2 for each patient will be analyzed together to identify changes in both CD30 tumor cells and other immune cell populations. Cells with mitochondrial read rate > 10% and < 200 detectable genes are considered as low-quality and filtered out. Unwanted sources of variation will be regressed out of the data by constructing linear models to predict gene expression based on the number of UMIs per cell as well as the percentage of mitochondrial gene content. Normalized and scaled data will be clustered using the top significant principal components of the highly variable genes. The t-distributed stochastic neighbor embedding (t-SNE) algorithm will be used to visualize the resulting clusters. Cluster specific markers will be identified to generate heatmap and identify cell types in each cell cluster. T cell subtype markers, such as T reg, memory T cells, effector T cells, exhausted T cells etc. will be used to identify different T cell populations. Chromium's V(D)J-Loupe will be used for analysis of TCR clonotypes and for visualization. Over-represented TCR clone in each patient will be identified and considered as indication of malignant cells. Genes will be compared between malignant and non-malignant cells using Bioconductor package "Limma" on log transformed and normalized scRNA-seq data. Gene Set Enrichment analysis (GSEA) v3 will be performed to evaluate the significance activation of the Hallmark and KEGG gene sets in MSigDb. This analysis will help us understand what specific pathways are activated in tumor cells and how the pathways are changing after treatment. Single cell trajectory analysis will be conducted with diffusion pseudotime method using Bioconductor package "destiny", which will capture the dynamic changes of tumor cells before and after treatment.

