1.3 Exploratory Objectives

- To generate a preliminary RNA signature associated with response of CD30+LYPDs cells to leflunomide.

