12.4 Statistical Analysis Plan

Patient demographic and baseline characteristics, including age, gender, medical history, and prior therapy, will be summarized using descriptive statistics. For continuous variables, descriptive statistics (number [n], mean, standard deviation, standard error, median, and range will be provided. For categorical variables, patient counts and percentages will be provided.

Observed toxicities will be summarized, in terms of type, grade, time of onset, duration, and attribution to the study treatment. The overall response rate and complete response rate will be calculated along with the Clopper Pearson binomial 95% exact confidence intervals. Duration of response will be calculated using Kaplan-Meier product limit estimator; median duration of response will also be estimated when possible.

The miRNA/mRNA expression profile data will be summarized by descriptive statistics. The data will also be used to explore the miRNA/mRNA that show significant differences between responders and non-responders after leflunomide treatment. For miRNA/RNA profiling, fold changes >3 with an FDR <0.05 will be considered significant.

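### The single-cell RNA analysis names no unit of analysis and no allowance for cells nested within 12 to 14 patients, so its stated error rate is not secured

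*Combined protocol and SAP*

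**What the plan says.** The only exploratory objective, in Section 1.3, is "To generate a preliminary RNA signature associated with response of CD30+LYPDs cells to leflunomide". Section 2.5 makes single-cell RNA sequencing part of the molecular analysis of response.

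Section 9.2.6 gives the method:

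- Pooling: "The samples at baseline and beginning of cycle 2 for each patient will be analyzed together". Whether patients are then combined is not said.
- Nuisance adjustment: "constructing linear models to predict gene expression based on the number of UMIs per cell as well as the percentage of mitochondrial gene content". Patient is not among the terms.
- Labelling of malignant cells: "Over-represented TCR clone in each patient will be identified and considered as indication of malignant cells".
- Test: "Genes will be compared between malignant and non-malignant cells using Bioconductor package" limma, on log-transformed, normalised data. No threshold is given here.
- Quality filter: "Cells with mitochondrial read rate > 10% and < 200 detectable genes are considered as low-quality and filtered out".

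Section 12.4 plans to explore differences between responders and non-responders, without naming a test or a unit, and adds that "fold changes >3 with an FDR <0.05 will be considered significant". The synopsis names yet another method for correlates of response: pathway identification with supervised principal components.

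Section 9.2.1 takes one lesion per patient at each timepoint. Section 12.2 plans 12 response-evaluable patients, with at most 14 accrued.

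**The concern.** Cells from one biopsy share a patient, a lesion and a processing run, so they are not independent observations on a question about patients. A response signature is such a question, and it has 12 to 14 independent units however many cells are sequenced. If cells serve as replicates, standard errors shrink with the cell count while variation between patients does not, and p-values and FDR values come out too small. The malignant versus non-malignant comparison carries a milder form of the same risk.

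At stake is whether the FDR threshold in Section 12.4 means what it says. Section 2.4 hopes that these data will inform future combinations and patient-specific treatment, so an uncontrolled error rate would be carried into later work.

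**Working it through.** **The plan's own figures.** No sample-size or error calculation is given for the RNA analysis. The figures in Section 12.2 for 12 patients reproduce. The Clopper-Pearson widths for 4 to 10 responders are 55.2, 57.2, 57.8, 57.2, 55.2, 51.7 and 46.3%. The chance of seeing at least one adverse event of 15% incidence is 1 − 0.85^12 = 85.8%.

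**Inputs.** From the documents: 12 patients, one lesion per timepoint, the fold-change threshold of 3 and the FDR threshold of 0.05. Assumed, because the documents give none: cells per patient, intra-patient correlation (ICC), variance of the contrast between patients, and log2 standard deviations (SD).

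**1. Between-patient contrast, cells as replicates.** With m cells per patient, the design effect is D = 1 + (m − 1) × ICC, and the actual error at nominal 5% is 2 × [1 − Φ(1.96/√D)].

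| m | ICC | D | Actual error |
|---|---|---|---|
| 100 | 0.001 | 1.099 | 6% |
| 100 | 0.01 | 1.99 | 16% |
| 100 | 0.10 | 10.9 | 55% |
| 300 | 0.01 | 3.99 | 33% |
| 300 | 0.10 | 30.9 | 72% |
| 1000 | 0.01 | 10.99 | 55% |
| 1000 | 0.10 | 100.9 | 85% |

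At 500 cells from each of 12 patients and ICC 0.10, D = 50.9, and 6,000 cells carry the information of 6,000/50.9 ≈ 118 independent ones.

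**2. Malignant versus non-malignant, within patient.** A patient effect shared by both cell classes cancels from the difference. With balanced counts the actual error is 2 × [1 − Φ(1.96/√(1 − ICC))]: 4.4%, 3.9% and 2.8% at ICC 0.05, 0.10 and 0.20, slightly conservative. Inflation arises only if the contrast varies between patients. With m cells per class, contrast variance τ² and cell variance σ², the variance ratio is R = 1 + mτ²/(2σ²), and R replaces D in the formula of step 1:

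- m = 150, τ²/σ² = 0.01: R = 1.75, error 14%.
- m = 150, τ²/σ² = 0.10: R = 8.5, error 50%.

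**3. Effect of the fold-change condition.** A fold change of 3 is log2(3) = 1.585. Take a gene with no true difference, 6 responders and 6 non-responders, 500 cells per patient and a cell-level SD of 1.5. The difference in group means then has variance (s² + 1.5²/500) × (1/6 + 1/6), where s is the between-patient log2 SD.

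| s | SD of difference | 1.585/SD | Null genes beyond threshold per 10,000 |
|---|---|---|---|
| 0.5 | 0.291 | 5.44 | under 0.01 |
| 0.8 | 0.464 | 3.42 | 6 |
| 1.0 | 0.579 | 2.74 | 62 |
| 1.2 | 0.694 | 2.28 | 224 |

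**4. Share of calls that are false.** This comes from a simulation of the responder contrast with 10,000 genes and 12 patients (6 versus 6 and 4 versus 8), 100 or 500 cells per patient, 1% or 5% of genes truly changed by a log2 fold change of 2, and six repeats per setting.

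- Cells as units, FDR <0.05 alone: 0.20 to 0.33 in the mildest setting (ICC 0.004, 100 cells), and 0.74 to 0.99 in all others.
- Cells as units, with fold change >3 added: 0 for s up to 0.5; 0.02 to 0.15 at 0.8; 0.13 to 0.57 at 1.0; 0.38 to 0.82 at 1.2.
- Patients as units, FDR <0.05: about 0.04 to 0.06 in most settings where more than a few genes are called.

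**The case against.** The documents never say that cells are treated as independent. limma can block on patient, and Section 9.2.6 speaks of analysing samples for each patient. If the comparison is run patient by patient, cells are a legitimate unit for describing that one sample. This stands: the defect is an omission, not a declared assumption of independence.

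The limma comparison and the FDR rule also sit in different sections and follow different contrasts, and the synopsis names a third method. It would be wrong to read Section 12.4 as thresholding the limma output of Section 9.2.6. That also stands, although the rule is introduced for RNA profiling generally and no section settles its scope.

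A reader might infer from the error rates in step 1 that the signature would consist mostly of false positives. The documents do not support that. Section 12.4 requires a large fold change as well as the FDR threshold. With that filter and some true signals, false calls outnumber true ones only when between-patient log2 SD is about 1.0 or more and true signals are few (about 1% of genes). No document says that such variation is present.

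Finally, every error figure rests on assumed correlations and cell counts, and at ICC 0.001 with 100 cells the inflation is slight. What the objection leaves untouched is that no section makes the patient the unit or models clustering by patient.

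**Conclusion.** The point holds as an unstated unit of analysis with a foreseeable consequence. Run with cells as replicates, the nominal 5% error would be about 16% to 55% per gene for a between-patient contrast, assuming 100 cells per patient and ICC 0.01 to 0.10, and higher with more cells. It would be about 14% to 50% for malignant versus non-malignant cells, assuming 150 cells per group and a contrast that varies between patients by 1% to 10% of the cell variance. Without such variation that second contrast is not inflated.

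The fold-change condition removes many false calls. The signature may therefore contain false positives, but a false majority is not shown. Severity is low: the objective is exploratory and labelled preliminary, and no primary or secondary endpoint depends on it.

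A separate minor point is the cell filter. It joins its two failure conditions with a conjunction, so read literally it keeps a cell that fails only one of them.

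**What to change.** In Sections 9.2.6 and 12.4:

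- Sum counts per patient, cell type and timepoint (pseudobulk).
- Run limma on these sums with patient as a block for malignant versus non-malignant and for baseline versus Cycle 2 Day 1. Base the timepoint contrast on patients with both samples. Section 9.2.2 takes the Cycle 2 sample only when lesions are present, so report how many patients lack one.
- Make the patient the unit for responder versus non-responder.
- Apply the fold-change and FDR rule to these tests, and label any cell-level result descriptive.
- Minor: reword the filter to exclude cells with mitochondrial reads above 10% or with fewer than 200 detectable genes.

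The cost is SAP wording, minor programming and fewer genes called. Power may be low. In the simulation with 6 versus 6 patients and a true log2 fold change of 2, the patient-level test under the full rule finds about 0.85 to 0.92 of true genes at between-patient SD 0.5, 0.07 to 0.50 at SD 0.8 and 0.01 to 0.14 at SD 1.0. That is what 12 patients can support if variation between patients is large.
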